### **6.2. Diet, Fluid, and Activity Control**

Matched-control healthy subjects are required to refrain from use of tobacco, smoking cessation products, and nicotine-containing products within 3 months prior to Screening through EOT or

ET. Hepatically impaired subjects are required to refrain from the use of tobacco- and nicotine-containing products within 2 hours prior to dosing and for 4 hours postdose.

Consumption of grapefruit, grapefruit juice, or Seville oranges from 14 days prior to dose administration (Day 1) and through EOT or ET or consumption of other fruit juices from 72 hours prior to dose administration and through EOT or ET will not be allowed unless deemed acceptable by the Covance Medical Monitor, Investigator (or designee), and Sponsor.

Subjects are required to abstain from consuming alcohol-, citric acid-, and caffeine-containing foods and beverages for 48 hours prior to Check-in (Day -1) and through EOT or ET, unless deemed acceptable by the Investigator.

Subjects will refrain from strenuous exercise from 5 days prior to Check-in (Day -1) and during the period of confinement at the clinical site and will otherwise maintain their normal level of physical activity through EOT or ET (ie, will not begin a new exercise program or participate in any unusually strenuous physical exertion).

While confined at the clinical site, subjects will receive a standardized diet at scheduled times that do not conflict with other study-related activities.

Doses of LOXO-292 will be preceded by a fast of at least 2 hours from food (not including water) and will be followed by a fast from food (not including water) for at least 1 hour postdose. Glucose tablets may be administered as needed for treatment of hypoglycemia. Subjects may consume water ad libitum.

## 7. STUDY ASSESSMENTS AND PROCEDURES

### 7.1. Pharmacokinetic Assessments

#### 7.1.1. Pharmacokinetic Blood Sample Collection and Processing

Blood samples for PK analysis of LOXO-292 plasma levels and protein binding and potential analysis of metabolites will be collected at the timepoints specified in [Appendix 5](#). The exact time of the study drug administration and the actual time of blood sampling for PK analysis and protein binding will be recorded on the eCRF.

Processing, storage, and shipping instructions for these PK blood and protein binding samples will be provided in a separate Laboratory Manual. The number of blood samples and total blood volume required for PK testing and protein binding is presented in [Appendix 3](#).

#### 7.1.2. Analytical Methodology

Concentrations of LOXO-292 in plasma will be determined using a validated bioanalytical method. Specifics of the bioanalytical methods will be provided in a separate document. The concentrations of total and unbound LOXO-292 will be determined in a sample of predose plasma fortified with a known concentration of LOXO-292. The unbound fraction will be calculated based on total and unbound LOXO-292 levels. Samples of plasma may be analyzed

for exploratory analyses of metabolites. If such analyses are conducted, the results will be reported separately by the Sponsor.

## 7.2. Safety and Tolerability Assessments

Safety evaluations may be repeated at the discretion of the Investigator (or designee), Covance Medical Monitor, or Sponsor.

Every effort will be made to schedule and perform the procedures in accordance with the nominal time, giving considerations to appropriate posture conditions, practical restrictions, and any other procedures to be performed at the same timepoint. The order of priority for scheduling procedures around a timepoint is (in descending order of priority):

- Dosing;
- Pharmacokinetic blood sampling;
- Vital signs assessments;
- Electrocardiograms;
- Blood and urine samples for clinical laboratories;
- Physical examination.

### 7.2.1. Adverse Events

Adverse event definitions; assignment of severity, causality, action taken, and outcome; and procedures for reporting SAEs are detailed in [Appendix 1](#).

Subjects will be asked a nonleading HDYF? question such as “Have there been any changes in your health status since Screening/since you were last asked?” at the timepoints specified in [Appendix 5](#) (ie, at Screening [after the ICF is signed], at Check-in (Day -1), at each postdose vital signs assessment, and at an appropriate time for all other days). Subjects will also be encouraged to voluntarily report AEs occurring at any other time through the EOS.

AEs, whether volunteered, identified by the subject’s responses to HDYF? inquiries, or noted on PE, ECG, vital signs assessments, or laboratory tests, will be recorded throughout the study (ie, from signing of the ICF until EOS [or ET if the subject discontinues from the study and does not complete a follow-up call]), either as subject medical history (if the event is reported as beginning prior to signing of the ICF or if the event occurs prior to study drug administration on Day 1 and is assessed as not related to study procedures by the Investigator [or designee]) or as AEs (if the event occurs after signing of the ICF but prior to study drug administration on Day 1 and is assessed as related to study procedures by the Investigator [or designee], or if the event occurs after study drug administration on Day 1 through EOT or ET regardless of relationship to study drug). From EOT or ET through EOS, only AEs assessed as related to study drug by the Investigator (or designee) are to be reported. All SAEs that develop from the time of ICF signing until EOS (or ET, if the subject discontinues from the study and does not complete a follow up call) are to be reported.

Unless a subject withdraws consent or is withdrawn from the study and does not complete the follow-up call, all subjects must be followed until EOS. Subjects with AEs that are assessed as related to study drug by the Investigator (or designee) which are ongoing at EOS may continue to be followed until the symptoms or value(s) return to normal, or acceptable levels, as judged by the Investigator or designee and confirmed by the Sponsor. The Investigator (or designee) should use appropriate judgment in ordering additional tests as necessary to monitor the resolution of events. The Sponsor may request that additional safety tests be performed.

Subjects will receive a Safety Follow-up phone call 7 days ( $\pm$  2 days) after EOT or ET to determine if any AE has occurred since the EOT or ET visit.

At all times, a subject may be required to remain at the clinical site for longer at the discretion of the Investigator (or designee).

Any event that meets the criteria of a Suspected Unexpected Serious Adverse Reactions (SUSAR) will be reported to the IRB/IEC according to site policy by the Investigator (or designee) and to regulatory authorities by the Sponsor (or Sponsor designee) according to regulatory authority requirements. Refer to Reference Safety Information in the current IB for LOXO-292 for expected adverse reactions.

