- To clarify the timing of the follow-up phone call to subjects from approximately 7 days after Clinic Discharge to 7 days ( $\pm$  2 days) after EOT or ET.

- To clarify that for subjects who terminate early and do not have a follow-up call, the AE reporting period ends at ET.
- To clarify that a withdrawn subject with an ongoing AE at ET will continue to be followed only if the AE is considered related to study drug.
- To clarify the timing requirements for reporting pregnancy in subjects or in the female partner of a subject.
- To update the timing window of the predose blood sample for unbound plasma concentrations of LOXO-292 so that it may be collected within 30 minutes prior to dosing, rather than within 15 minutes.
- To update the referenced version of the Investigator's Brochure to the current version.

The version number, date, and other minor typographical or formatting errors were also updated or corrected but do not affect the proposed conduct of the study.

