#### 1.6 Reporting

Food and Drug Administration-reportable AEs are AEs that are associated with the use of the drug and represent events that are assessed as serious, related, and unexpected. Food and Drug Administration-reportable AEs will be reported by the clinical site to the Sponsor, the Covance Medical Monitor, and the responsible Institutional Review Board (IRB). Final determination of whether an event represents a SUSAR will be the responsibility of the Sponsor.

Within 24 hours of when an AE that is potentially FDA-reportable is first recognized or reported, and within 24 hours of any SAE (regardless of whether the event is assessed as related or unrelated to study drug) being first recognized or reported, the Sponsor’s clinical safety

representative will be notified by the Investigator or designee in writing (eg, facsimile) using the following eFax number or email:

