e Electrocardiograms will be collected after the subject has rested in the supine position for at least 10 minutes, and will be obtained prior to and as close as possible to the scheduled blood draws.

f Vital signs measurements (oral temperature, respiratory rate, and supine blood pressure and heart rate [HR]) will be obtained at Screening and Check-in (Day -1), predose, at 2 hours ( $\pm$  10 minutes) and 4 hours ( $\pm$  10 minutes) postdose, and at each Study Day through EOT (or ET). Vital signs measurements should be carried out prior to and as close as possible to having blood drawn. Blood pressure and HR will be measured using the same arm for each reading after the subject has been supine for at least 5 minutes.

g An HDYF? inquiry performed at Screening (after the Informed Consent Form is signed), at Check-in (Day -1), at each postdose vital signs assessment, and at an appropriate time for all other days.

h AEs and SAEs will be collected beginning at informed consent. AEs will be recorded throughout the study (ie, from signing of the Informed Consent Form [ICF] until EOS, or until ET if the subject discontinues from the study and does not complete a follow-up call), either as subject medical history (if the event is reported as beginning prior to signing of the ICF or if the event occurs prior to study drug administration on Day 1 and is assessed as not related to study procedures by the Investigator [or designee]) or as AEs (if the event occurs after signing of the ICF but prior to study drug administration on Day 1 and is assessed by the Investigator [or designee] as related to study procedures, or if the event occurs after study drug administration on Day 1 through EOT or ET regardless of relationship to study drug). From EOT or ET through EOS, only AEs assessed as related to study drug are to be recorded. All SAEs that develop from the time of ICF signing until EOS (or ET if the subject discontinues from the study and does not complete a follow-up call) are to be reported.

i Dose administration is to be given during the morning of Day 1.

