j Primary PK blood samples will be collected prior to dosing (within 30 minutes) and 0.5, 1, 1.5, 2, 3, 4, 6, 8, 10, 12, 24, 48, 72, 96, 120, 144, 168, 192, 216, and 240 hours postdose (Day 11). The allowed sampling window for PK blood samples will be the following: within 15 minutes prior to dosing for the predose sample timepoint;  $\pm$  5 minutes for sampling timepoints within the first 12 hours;  $\pm$  30 minutes for sampling timepoints > 12 hours < 36 hours; and  $\pm$  60 minutes for the sampling timepoints ranging from 48 to 240 hours.

k For assessment of unbound plasma concentrations of LOXO-292, a blood sample will be collected predose (ie, within 30 minutes prior to dosing).

l Clinical chemistry panel (fasted at least 8 hours), coagulation parameters, complete blood count, and urinalysis will be performed at Screening, Check-in (Day -1), 24 hours postdose (Day 2), Day 5, Day 8, and at EOT (Day 11) or ET.

m Hemoglobin A1c test performed at Screening for subjects with hepatic impairment only.

n Alcohol breath test and drugs of abuse urine test. Results from the alcohol and drug tests will be used to determine subject eligibility per the inclusion/exclusion criteria.

o Prior and concomitant medication administration will be recorded beginning at informed consent. In addition, all Investigator-approved medications taken by a subject within 30 days prior to study drug administration for prescription medications, and 14 days prior to study drug administration for nonprescription medications, will be recorded on the subject's electronic Case Report Form.

p Female subjects only.

q Postmenopausal female subjects only.

r EOT is defined as when the subject is released from the CRU following completion of all assessments through Day 11. ET is defined as when the subject is released from the CRU if the subject terminates the study early. Vital sign, ECG, and safety laboratory results for serum chemistry, hematology, coagulation, and urinalysis are to be available for review by the Investigator or designee prior to subject release from the CRU at the EOT or ET visit.

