s To be performed 7 days ( $\pm$  2 days) following EOT or ET. End of Study (EOS) is defined as when the CRU contacts the subject by a follow-up phone call 7 days ( $\pm$  2 days) after the EOT visit or ET visit to determine if any SAE or study drug-related AE has occurred since the EOT or ET visit. All subjects who received LOXO-292 (including subjects who terminate the study early) will be contacted.

---

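### For a subject who leaves early, the required SAE reporting period depends on completing the follow-up call, so an SAE that prevents the call falls outside it

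*Protocol*

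**What the plan says.** **End of the SAE period.** Protocol Version 2, Section 7.2.1, has SAEs that develop from consent onward reported "until EOS (or ET, if the subject discontinues from the study and does not complete a follow up call) are to be reported". The Synopsis and Section 3.1 carry the same rule. Appendix 5 footnote h repeats the exception: "or ET if the subject discontinues from the study and does not complete a follow-up call) are to be reported".

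**What the two end points are.** Footnote r: "ET is defined as when the subject is released from the CRU if the subject terminates the study early". Footnote s: "End of Study (EOS) is defined as when the CRU contacts the subject by a follow-up phone call 7 days" (± 2 days) after the EOT or ET visit. Section 7.2.1 gives the same timing for the call.

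**Intent.** The summary of amended changes states the purpose: "To clarify that for subjects who terminate early and do not have a follow-up call, the AE reporting period ends at ET". Section 7.2.1 also exempts a withdrawn subject without a completed call from being followed to EOS.

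**Text that points the other way.**
- Footnote s adds: "All subjects who received LOXO-292 (including subjects who terminate the study early) will be contacted".
- Appendix 1, 1.6 asks that the sponsor's safety representative be notified "within 24 hours of any SAE (regardless of whether the event is assessed as related or unrelated to study drug) being first recognized or reported", and gives no end date.
- The letter of administrative change on SAE reporting, and SAP Section 6, run SAE reporting to Study Completion (the last subject's follow-up call) with no ET exception.

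**The concern.** The length of a safety reporting period should not be decided by the events it is meant to capture. Here it can be. Whether an early leaver completes the call depends partly on what happens after release. A subject who has died cannot complete it, and one who is in hospital may not be reachable. The exception treats these cases like a refusal or a loss of contact, so the gap is not random with respect to outcome.

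Safety is one of the two study objectives. Section 3.3 of the protocol names the liver as a possible target of toxicity, and each impairment group holds at most 8 subjects. In groups of that size, one SAE that nobody is required to report would matter to the description of that group.

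**Working it through.** No sample size, power or alpha figure is involved. The check reads the period rule together with the definitions and then looks for text that would keep the period open after a missed call.

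**Step 1. Length of the period.** The call is due 7 ± 2 days after EOT or ET, so 7 − 2 = 5 to 7 + 2 = 9 days. EOT is Day 11, so a completer's call falls on Day 11 + 5 = 16 to Day 11 + 9 = 20.

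| Subject | Required SAE period ends at | Days past release |
|---|---|---|
| Completer, call completed | EOS (Day 16 to 20) | 5 to 9 |
| Completer, call missed | no fallback stated | not defined |
| Early leaver, call completed | EOS | 5 to 9 |
| Early leaver, call not completed | ET | 0 |

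The last two rows differ only in whether the call was completed, which is known only afterwards.

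**Step 2. A hypothetical case.** A subject is released early on Day 2 and dies on Day 6. The call was due between Day 2 + 5 = 7 and Day 2 + 9 = 11 and cannot take place. The period reverts to Day 2, and the death lies 6 − 2 = 4 days beyond it. Had the subject lived and taken the call, a serious event with onset on Day 6 would have been inside.

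**Step 3. Does other text reopen the period?**
- Footnote s plans contact with every dosed subject but says nothing about a contact that fails. Section 7.2.1 supplies that fallback, and it is ET.
- Appendix 1, 1.6 sets how fast a known SAE is notified. It does not set a collection period.
- The letter would place the Day 6 death inside the period as long as the last subject's call is still to come. But it refers to page 36, which is where the Version 1 table of contents puts Section 7.2.1 (Version 2 puts it on page 56), and the wording it replaces is Version 1 wording. It does not amend the Version 2 sentence.
- SAP Section 6 also ends at Study Completion. SAP Section 4 says the plan was written from Protocol Version 1.0.

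Nothing in Version 2 keeps the period open after a missed call, and the letter and the SAP give a different end.

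**The case against.** The strongest answer is the letter. It addresses this subject directly, has all SAEs reported through Study Completion, and gives as its reason the removal of contradictory text. Its date is not in the text available, so which wording governs which subjects cannot be settled here. If the letter governs everywhere, it contradicts four places in Version 2 that still carry the exception. It shows what the sponsor wants but does not correct those places.

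Second, the rule does not forbid reporting. A site that hears of a death from a relative or a hospital could well notify it under Appendix 1, 1.6. SAP Section 10.5.1 lists every AE captured in the database and defines a treatment-emergent AE with no end date, so a notified event that was entered would be tabulated. This stands. A reader might infer that such events are dropped from the safety tables; the documents support only that the period rule does not require them to be reported.

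Third, ending at ET was deliberate, and early leavers are not released without checks: Section 4.6 calls for efforts to complete the final assessments, and footnote r wants safety results available before release. Neither reaches an event with onset after release.

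A reader might also infer that the interim safety reviews are biased by this rule. The documents do not support that. Those reviews are triggered by subjects who have finished all assessments including the call (Synopsis; SAP Section 11), so an early leaver without a call would not count toward the trigger whatever the SAE period. Any gap there comes mainly from the completion rule.

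**Conclusion.** The point holds in a narrow form. Under Version 2, the required SAE period for an early leaver ends 5 to 9 days after release if the call is completed and at release if it is not. An SAE that itself prevents the call therefore falls outside the period. Separately, Version 2 disagrees with the letter and with SAP Section 6 on when SAE reporting ends for these subjects.

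The limits are these. The exception does not apply to subjects who complete Day 11. A hospitalised subject who is still reached by phone stays covered. A reader might conclude that SAE counts by hepatic group will be biased toward safety, most of all in the group with the most early exits. The direction is plausible if such events go unreported, but the documents give no early-exit rate and no missed-call rate, so neither the size nor the distribution across groups can be stated. The primary pharmacokinetic comparison is not affected.

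**What to change.** Reconcile Protocol Version 2 (Synopsis, Section 3.1, Section 7.2.1 and Appendix 5 footnote h) with the letter and SAP Section 6.

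1. Remove the ET exception for SAEs.
2. End the SAE period for every dosed subject at a point that does not require a completed call. One option is the last day of the existing call window (EOT or ET plus 9 days), or the actual call if earlier. A call that took place shortens the period only once the subject's status is known. This also gives a defined end for a completer who misses the call. In the hypothetical case the period would run to Day 2 + 9 = 11 and include the Day 6 death.
3. State that any SAE with onset in that period is reported, from whatever source the site learns of it and whether or not the call was completed, subject to withdrawal of consent to data collection.
4. Record each call not completed and the reason.

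If Study Completion is preferred as the end, as in the letter, use it in all of these places. The cost is wording only, since the call is already planned and no visit is added. The downside is possibly a few more SAE reports.

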### **7.2.2. Clinical Laboratory Evaluations**

Clinical laboratory evaluations (clinical chemistry panel [fasted at least 8 hours], coagulation parameters, CBC, thyroid-stimulating hormone, hemoglobin A1c [hepatic subjects only], and UA) will be collected at the timepoints specified in [Appendix 5](#).

Screens for HCV antibody, HBsAg, and HIV antibody will be performed at Screening. A drug screen for selected drugs of abuse will be performed at Screening and repeated at Check-in (Day -1; including an alcohol breath test for all subjects and, for matched-control healthy subjects only, including cotinine). A serum qualitative pregnancy test (females only) and a follicle-stimulating hormone test (postmenopausal females only) will be performed at the timepoints specified in [Appendix 5](#).

The number of blood samples and total blood volume required for clinical laboratory evaluations is presented in [Appendix 3](#). A list of the specific evaluation is in [Appendix 2](#).

### **7.2.3. Vital Signs**

Vital signs (including oral temperature, respiratory rate, and supine BP and HR) will be obtained at the timepoints specified in [Appendix 5](#).

Blood pressure and HR measurements should be performed using the same arm for each reading and measurements should be taken after the subject has been resting in the supine position for at least 5 minutes.

When vital signs assessments are scheduled at the same time as blood draws, the blood draws will be obtained at the scheduled timepoint, and the vital signs will be obtained prior to and as close as possible to the scheduled blood draw.

#### **7.2.4. 12-Lead Electrocardiogram**

A 12-lead ECG (including PR, RR, QRS, and QT interval parameters) will be obtained after the subject has been resting for at least 10 minutes in the supine position at the timepoints specified in [Appendix 5](#). The QT interval will be corrected for HR by Fridericia's ( $QTcF = QT/[RR]^{1/3}$ ) formulae.

When 12-lead ECGs are scheduled at the same time as blood draws, the blood draws will be obtained at the scheduled timepoint, and the 12-lead ECGs will be obtained prior to and as close as possible to the scheduled blood draw.

